**Schedule of events Part 2**

Table 2: Part 2 Schedule of Activities for Subjects Randomized to Receive Sham Procedure in Part 1																	
Study Period	Part 2 Treatment/Follow-Up																
Study Day	Day 1			Day 2 	Day 15 (±1 day)			Day 16 	Day 29 (±1 day)			Day 30 	Days 64, 183, 302, 421, 540, 659, 778 (±7 days) 			Days 65, 184, 303, 422, 541, 660, 779 	Part 2 Final Follow-Up (Day 897 [±7 days])  or Part 2 Early Termination 
	Predose 	LP	Postdose		Predose	LP	Postdose		Predose	LP	Postdose		Predose	LP	Postdose		
Immunogenicity Sample	X 												X 				X
CSF PK 	X 				X				X				X				
Plasma PK 			X 										X 				X
Study Treatment Injection		X				X				X				X			
Inpatient Stay 			X														
Telephone Contact for Safety Monitoring (+3 Days)								X				X				X	
HINE and WHO Motor Milestone													X				X
Clinical Global Impression of Change and ACEND													X				X

**Schedule of events Part 2**

Table 2: Part 2 Schedule of Activities for Subjects Randomized to Receive Sham Procedure in Part 1																	
Study Period	Part 2 Treatment/Follow-Up																
Study Day	Day 1			Day 2 	Day 15 (±1 day)			Day 16 	Day 29 (±1 day)			Day 30 	Days 64, 183, 302, 421, 540, 659, 778 (±7 days) 			Days 65, 184, 303, 422, 541, 660, 779 	Part 2 Final Follow-Up (Day 897 [±7 days])  or Part 2 Early Termination 
	Predose 	LP	Postdose		Predose	LP	Postdose		Predose	LP	Postdose		Predose	LP	Postdose		
Optional Sibling SMA Data Collection 	X																X
Con Med Recording 	X-----X																
Adverse Event Collection 	X-----X																

ACEND = Assessment of Caregiver Experience with Neuromuscular Disease; AE = adverse event; Bi-PAP = bilevel positive airway pressure; Con Med = concomitant medication; CSF = cerebrospinal fluid; ECG = electrocardiogram; HINE = Hammersmith Infant Neurological Examination; LP = lumbar puncture; PK = pharmacokinetic(s); SAE = serious adverse event; WHO = World Health Organization.

 After the injection of study treatment on Day 1, subjects will remain at the study site for at least 24 hours (Day 2) for safety monitoring. There will be safety monitoring through telephone contact on the day following the injection of study treatment (i.e., Days 16, 30, 65, 184, 303, 422, 541, 660, and 779). During that telephone contact, changes in concomitant medications and AEs, information on the subject's daily ventilator/Bi-PAP use, and health status will be recorded.

 If the study continues beyond Year 2 (i.e., beyond Day 778), then from Day 897 onwards, subjects will maintain evaluations for study treatment injection every 4 months with the schedule of events for those additional timepoints to alternate between the assessments done on Day 183 and those done on Day 302. Day 302 assessments would be performed at Day 897 and Day 183 assessments would be performed at Day 1016. That pattern would continue until the end of the study. Part 2 Final Follow-up Evaluation would then occur approximately 4 months after the last injection of study treatment.

-  The Part 2 Final Follow-up Evaluation will occur 4 months after the last injection of study treatment, which will either be on Day 778 or later, if Part 2 of the study continues beyond Year 2.
-  Subjects who terminate early will be encouraged to complete the safety evaluations scheduled for the Part 2 Early Termination Evaluation.
-  Inclusion/Exclusion Criteria, Informed Consent, and CSF PK must be performed on Part 2 Day 1 predose.
-  Vital signs include resting systolic and diastolic blood pressure, pulse rate, respiratory rate, temperature, pulse oximetry, and transcutaneous carbon dioxide. Pulse oximetry and transcutaneous carbon dioxide will be measured predose at each evaluation.
-  If Part 2 Day 1 study treatment injection is delayed more than 24 hours after the End of Part 1 visit, the following procedures must be done on Part 2 Day 1 predose: vital signs, weight, growth parameters, physical examination, ventilator use, neurological examination, and CSF PK. If Part 2 Day 1 study treatment injection is delayed more than 24 hours after End of Part 1 due to an AE, SAE, or other safety concern, or if Part 2 Day 1 study treatment injection is delayed more than 30 days after End of Part 1 for any reason, the following procedures must be done on Part 2 Day 1 predose: vital signs, weight, growth parameters, physical examination, ventilator use, neurological examination, ECG, CSF PK, and safety laboratory tests. Immunogenicity testing must also be repeated if Part 2 Day 1 study treatment injection is delayed more than 30 days after End of Part 1 for any reason.
-  Vital signs (resting systolic and diastolic blood pressure, pulse rate, respiratory rate, temperature, and pulse oximetry) will be collected at 4 timepoints: 1, 2, 4, and 6 hours (all  $\pm 15$  minutes) after the injection of study treatment only on Part 2 Day 1. On subsequent study days, vital signs will be collected 1 hour after the injection of study treatment.
-  Vital signs (resting systolic and diastolic blood pressure, pulse rate, respiratory rate, temperature, and pulse oximetry) will be collected on Day 2 within 20 to 24 hours after the injection of study treatment only.
-  At the evaluations scheduled for injection of study treatment, subjects will be assessed for the following growth parameters: body length, head circumference, chest circumference, and arm circumference. Growth parameters and weight are to be collected at the same time.
-  Neurological examinations include assessment of mental status, level of consciousness, sensory function, motor function, cranial nerve function, and reflexes. If sedation was used, please allow sufficient recovery time for the subject to be fully engaged in the examination because it is important that the data collected truly reflect the subject's neurological performance.
-  Predose and postdose.
-  ECG will be performed at Days 64, 183, 540, and 778, and at the Part 2 Final Follow-up Evaluation. ECG must be performed before obtaining blood samples for safety laboratory tests.
-  Blood chemistry, hematology, urinalysis, urine total protein panels, and coagulation parameters. Urine total protein and coagulation parameters will be assessed by local laboratories.
-  Samples for safety laboratory tests will be collected before the injection of study treatment at each dosing visit.
-  Blood samples for immunogenicity testing will be collected before the injection of study treatment on Days 64, 183, 302, 421, 540, 659, and 778.
-  Refer to [Error! Reference source not found.](#) for CSF PK sample schedule. The CSF samples will be analyzed for Nusinersen concentrations. The remaining CSF sample will be stored for optional future biomarker analyses.
-  Blood samples for PK assessment will be collected 4 hours ( $\pm 1$  hour) after the injection of study treatment only on Day 1. Refer to [Error! Reference source not found.](#) for the plasma PK sample schedule. Plasma PK samples will be collected predose on Days 64, 183, 540, and 778.
-  Overnight stay (at least 24 hours) is required after the first injection of study treatment. Following all subsequent injections, a stay of at least 1 hour at the study site is required; overnight stays are optional on these days.

The optional assessment of sibling SMA data collection will be performed only after obtaining consent.

In addition to concomitant medications, ancillary procedures will be recorded.

AEs and SAEs will be collected in the case report form from the time of signing of the informed consent form described in Section and Section 15.3.2 of the protocol.

### PK Part1

Table 3 Part 1 Pharmacokinetic Sampling Schedule				
Treatment Period	Part 1 Study Day	Timepoints	Blood Collection (mL)	CSF Collection (mL)
Multiple Dose: LP Injection	Day 1	Predose	NA	0.5
		4 h ( $\pm$ 1 h) postdose	0.5	NA
	Day 15	Predose	NA	0.5
	Day 29	Predose	NA	0.5
	Day 64	Predose	0.5	0.5
	Day 183	Predose	0.5	0.5
	Day 302	Predose	NA	0.5
	End of Part 1	NA	0.5	NA

CSF = cerebrospinal fluid; h = hour; min = minutes; LP = lumbar puncture; mRNA = messenger ribonucleic acid; NA = not applicable (no collection scheduled); SMA = spinal muscular atrophy.

 Details on sampling, preparation, and shipment are included in the Study Laboratory Manual.

 Upon consent, the collected CSF samples from the study subjects will be stored for future investigation of possible biomarkers of SMA disease (e.g., CSF mRNA, CSF protein, CSF microRNA panel), for profiling of study drug binding proteins, bioanalytical method validation purposes, stability assessments, metabolite assessments, and immunogenicity assessments (including assay development and validation purposes), or for assessing other actions of Nusinersen with plasma and CSF constituents.

### PK Part2

Table 4 Part 2 Pharmacokinetic Sampling Schedule for Subjects Randomized to Receive Nusinersen in Part 1				
Treatment Period	Part 2 Study Day	Timepoints	Blood Collection (mL)	CSF Collection (mL)
Multiple Dose: LP Injection	Day 1	Predose	NA	0.5
		4 h ( $\pm$ 1 h) postdose	0.5	NA

**PK Part2**

	Day 120	Predose	NA	0.5
	Day 239	Predose	0.5	0.5
	Day 358	Predose	NA	0.5
	Day 477	Predose	0.5	0.5
	Day 596	Predose	NA	0.5
	Day 715	Predose	0.5	0.5
	Part 2 Final Follow-Up	NA	0.5	NA

CSF = cerebrospinal fluid; h = hour; min = minutes; LP = lumbar puncture; mRNA = messenger ribonucleic acid; NA = not applicable (no collection scheduled); SMA = spinal muscular atrophy.

 Details on sampling, preparation, and shipment are included in the Study Laboratory Manual.

 Upon consent, the collected CSF samples from the study subjects will be stored for future investigation of possible biomarkers of SMA disease (e.g., CSF mRNA, CSF protein, CSF microRNA panel), for profiling of study drug binding proteins, bioanalytical method validation purposes, stability assessments, metabolite assessments, and immunogenicity assessments (including assay development and validation purposes), or for assessing other actions of Nusinersen with plasma and CSF constituents.

**PK Part 2**

Table 5 Part 2 Pharmacokinetic Sampling Schedule for Subjects Randomized to Receive Sham Procedure in Part 1				
Treatment Period	Part 2 Study Day	Timepoints	Blood Collection (mL)	CSF Collection (mL)
Multiple Dose: LP Injection	Day 1	Predose	NA	0.5
		4 h ( $\pm$ 1 h) postdose	0.5	NA
	Day 15	Predose	NA	0.5
	Day 29	Predose	NA	0.5
	Day 64	Predose	0.5	0.5
	Day 183	Predose	0.5	0.5
	Day 302	Predose	NA	0.5
	Day 421	Predose	NA	0.5

## PK Part 2

	Day 540	Predose	0.5	0.5
	Day 659	Predose	NA	0.5
	Day 778	Predose	0.5	0.5
	Part 2 Final Follow-Up	NA	0.5	NA

CSF = cerebrospinal fluid; h = hour; min = minutes; LP = lumbar puncture; mRNA = messenger ribonucleic acid; NA = not applicable (no collection scheduled); SMA = spinal muscular atrophy.

 Details on sampling, preparation, and shipment are included in the Study Laboratory Manual.

 Upon consent, the collected CSF samples from the study subjects will be stored for future investigation of possible biomarkers of SMA disease (e.g., CSF mRNA, CSF protein, CSF microRNA panel), for profiling of study drug binding proteins, bioanalytical method validation purposes, stability assessments, metabolite assessments, and immunogenicity assessments (including assay development and validation purposes), or for assessing other actions of Nusinersen with plasma and CSF constituents.

## Description of Objectives and Endpoints

### 1.1 Primary Objectives and Endpoints

#### Part 1

The primary objective of Part 1 of this study is:

- To assess the safety and tolerability of Nusinersen in subjects with SMA who are not eligible to participate in the clinical studies ISIS 396443-CS3B or ISIS 396443-CS4.

The endpoints that relate to this objective are:

- Incidence of adverse events (AEs) and serious adverse events (SAEs)
- Change from baseline (see [Section 5](#)) in clinical laboratory parameters, electrocardiograms (ECGs), vital signs, and growth parameters
- Change from baseline (see [Section 5](#)) in neurological examination outcomes

#### Part 2

The primary objective of Part 2 of this study is:

- To assess the long-term safety and tolerability of Nusinersen in subjects with SMA who participated in Part 1 and completed their End of Part 1 Evaluation assessments.

The endpoints that relate to this objective are:

- Incidence of AEs and SAEs
- Change from baseline (see [Section 5](#)) in clinical laboratory parameters, ECGs, and vital signs
- Change from baseline (see [Section 5](#)) in neurological examination outcomes
- Coagulation parameters (activated partial thromboplastin time [aPTT], partial thromboplastin time [PTT], and international normalized ratio [INR]) and urine total protein

## **1.2 Secondary Objectives and Endpoint**

The secondary objective and endpoint of Part 1 of this study are as follows:

- To examine the pharmacokinetics (PK) of Nusinersen in subjects with SMA who are not eligible to participate in the clinical studies ISIS 396443-CS3B or ISIS 396443-CS4
- Nusinersen concentrations in plasma and cerebrospinal fluid (CSF)

The secondary objective and endpoint of Part 2 of this study are as follows:

- To examine the PK of Nusinersen in subjects with SMA who participated in Part 1 and completed their End of Part 1 Evaluation assessments
- Nusinersen concentrations in plasma and CSF
- Plasma antibodies to Nusinersen

## **1.3 Exploratory endpoints**

### **Part 1**

The exploratory objective of Part 1 of this study is:

- To explore the efficacy of Nusinersen in subjects with SMA who are not eligible to participate in the clinical studies ISIS 396443-CS3B or ISIS 396443-CS4.

The endpoints that relate to this objective are:

- Change from baseline in ventilator use
- Attainment of motor milestones assessed by Section 2 of the Hammersmith Infant Neurological Examination (HINE)

- Change from baseline in growth parameters (body length, head circumference, chest circumference, arm circumference, weight for age, weight for length, and head to chest circumference ratio) through final safety follow-up evaluation
- Clinical Global Impression of Change (physician and caregiver assessment) through final safety follow-up evaluation
- Plasma antibodies to Nusinersen

## **Part 2**

The exploratory objective of Part 2 of this study is:

- To explore the efficacy of Nusinersen in subjects with SMA who participated in Part 1 and completed their End of Part 1 Evaluation assessments.

The endpoints that relate to this objective are:

- Change from baseline in ventilator use
- Attainment of motor milestones assessed by World Health Organization (WHO) motor milestones and Section 2 of the HINE
- Change from baseline in growth parameters (body length, head circumference, chest circumference, arm circumference, weight for age, weight for length, and head to chest circumference ratio) through Part 2 Final Follow-up Evaluation
- Clinical Global Impression of Change (physician and caregiver assessment) through Part 2 Final Follow-up Evaluation and Assessment of Caregiver Experience with Neuromuscular Disease (ACEND)

## **2 Statistical Methods: General Considerations**

In this SAP, the terms “control” and “previous control” refer to the set of subjects who were randomized to undergo the sham procedure during the Part 1.

In order to distinguish nominal visit names from duration defined in days, visit names will be referred to as “Day 15”, “Day 29”, etc., and “15 days” or “29 days” etc. will be used to define time intervals.

Due to emergent data from the Nusinersen clinical development program, the subjects in Part 1 ended the study early as follows: subjects randomized to sham terminated Part 1 first irrespective of Part 1 planned dosing days and subjects randomized to Nusinersen transitioned to Part 2 accordingly to their specific dose schedule. Part 2 was also terminated early to allow subjects to

enter the ISIS 396443-CS11 study. For these reasons, the actual study day associated with visits Part 1 and Part 2 will vary widely amongst subjects. Therefore, a windowing schema will be implemented for by visit analyses (see [section 4.1](#))

The safety population will include all subjects who are randomized and receive at least 1 dose of study treatment or sham procedure. Subjects randomized to receive sham procedure but incorrectly treated with Nusinersen will be counted in the ISIS 396443 group from the first dose of Nusinersen received.

The Efficacy set at each visit will be defined as the subset of subjects in the Safety set who has had the opportunity to be assessed at that visit (actual visit for Part 2 or windowed visit for integrated analysis see [section 4.1](#))

The PK population will include all subjects who are randomized and have at least 1 evaluable post dose or post sham-procedure PK sample.

The immunogenicity population will include all subjects who are randomized and have at least 1 evaluable post dose or post sham-procedure immunogenicity data.

For all time-to-event endpoints, (e.g., time to death or permanent ventilation), the date of first dose/sham administration will be used as the reference time point. If the date of first dose/sham procedure is incomplete, the date of randomization will be used.

Summary statistics will be presented throughout. For continuous endpoints, summary statistics will generally include number of subjects with data, mean, standard deviation, median, minimum and maximum. The mean changes from baseline will be estimated with 95% confidence intervals. For categorical endpoints, summary statistics will generally include: number of subjects dosed, number of subjects with data, and the percentage of those with data in each category. Frequency distributions will be presented as appropriate.

The statistical software, SAS® version 9.4 or above, will be used for all summaries and statistical analyses.

For Part 2, a limited number of summaries will be produced. The approach will be to preserve the Part 1 study groupings as follows for Safety and Efficacy population:

- Previous control.
- Previous ISIS 396443.
- Total (previous control and previous ISIS 396443).

For the integrated analyses, the Safety displays will be grouped as follows:

- Previous control, Part 1, from their first sham procedure in Part 1.
- Previous control, Part 2, from their first ISIS 396443 dose in Part 2.
- Previous ISIS 396443, Part 1 and 2, from their first ISIS 396443 dose in Part 1.
- Total (Previous control Part 2 and previous ISIS 396443 Part 1 and 2)

For the integrated analyses, the Efficacy displays will be grouped as follows:

- Previous control, Part 1, from their first sham procedure in Part 1.
- Previous control, Part 2, from their first ISIS 396443 dose in Part 2.
- Previous control, Part 1 and 2, from their first sham procedure in Part 1.
- Previous ISIS 396443, Part 1 and 2, from their first ISIS 396443 dose in Part 1.

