## 1 Study Design

This is a Phase 2 multicenter study conducted in 2 parts.

Part 1 was originally designed as a randomized, double-blind, sham-procedure controlled study to assess the safety and tolerability and explore the efficacy of intrathecally administered Nusinersen (also known as ISIS 396443 and BIIB058) over a period of approximately 14 months (from the first dose until the End of Part 1 Evaluation). Up to 21 subjects were randomized in a ratio of 2:1 to receive Nusinersen by intrathecal lumbar puncture (LP) injection or a sham-procedure control. Randomization was stratified based on age at onset of clinical signs and symptoms consistent with SMA: >6 months versus ≤6 months. Part 1 of the study was stopped early due to the efficacy results seen in the ISIS 396443-CS3B study and the planned analysis of Part 1 is described in a separate Statistical Analysis Plan and corresponding CSR.

Part 2 study procedures will be determined based on the treatment assignment in Part 1.

For subjects who were randomized to receive Nusinersen in Part 1, Part 2 Day 1 will occur following the End of Part 1 Evaluation or approximately 4 months following the last injection of Nusinersen in Part 1. On Part 2 Day 1, subjects will undergo predose evaluations according to the schedule of events and then receive their first dose of Nusinersen for Part 2 (next maintenance dose). Subjects will return to the study site on Days 120, 239, 358, 477, 596, and 715 for follow-up evaluations and subsequent maintenance dose injections. For subjects who were receiving sham procedure in Part 1, Part 2 Day 1 will occur following the End of Part 1 Evaluation or as soon as possible following the End of Part 1 Evaluation. At Day 1, subjects will undergo predose evaluations according to the schedule of events and then receive their first dose of Nusinersen (first loading dose). Subjects will return to the study site on Days 15, 29, 64, 183, 302, 421, 540, 659, and 778 for follow-up evaluations and subsequent injections. All subjects will terminate early Part 2 for enrollment in open-label extension study, ISIS 396443-CS11.

This statistical analysis plan (SAP) describes the analyses planned for the entire study (integration of Part 1 and Part 2) and additionally some summaries of Part 2 data only.

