### **3.3 Extent of Exposure**

The number of doses and or/ sham procedures will be summarized using frequency distributions. The amount of Nusinersen received will be summarized using summary statistics.

Overall time on study will be defined as the total number of days a subject is known to be followed on study and will be calculated as follows:

Overall time on study = (Last date on study) – (Date of first dose or first sham procedure) + 1.

The last date on study is defined as the date of the latest visit or evaluation or telephone contact, or time of death from all available data for a given subject.

Given the long half-life of Nusinersen, subjects are considered to be exposed to study drug from the time the first dose was administered to the last day of follow-up. Essentially, exposure is equivalent to time on study.

The dosing and time on study will be summarized only for Part 2 and integrated data.

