- if the start time is missing and the start date is same as the first dosing date, then the event is considered to have occurred on or after the first dose of study treatment.

If it cannot be determined whether an event has occurred on or after dosing due to a missing or partial date, then the event will be assumed to have occurred on or after the first dose for the purpose of identifying treatment-emergent AEs.

Due to the long half-life of Nusinersen, analyses of treatment-emergent AEs will include all events reported during the study.

AEs will be coded using the MedDRA dictionary. This coding system provides more than five levels to classify adverse events. In general, adverse events will be presented by system organ class and preferred terms but other classifications may be used if warranted.

The incidence of treatment-emergent AEs will be summarized. A subject having the same AE more than once will be counted only once in the incidence for that AE. The summary tables will include incidence estimates for overall system organ class as well as for preferred terms within each system organ class. Incidence will be presented by decreasing order by system organ class and by decreasing order by preferred term within each system organ class. The most common AEs, i.e., those that occurred in at least 3 subjects, will be presented. Upon examination of the actual data, different cut-offs may be used if it is deemed more appropriate.

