#### **5.1.3 Serious adverse events**

The incidence of treatment-emergent SAEs will be summarized by time of onset by 3-month time intervals. All SAEs will be listed including any that occurred prior to commencement of study treatment.

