### **5.1.6 Presentations**

The following presentations will be shown for the integrated analysis:

- an overall summary showing, the number and percentage of subjects with an AE, a moderate or severe event, a severe event, a possibly or related event, a related event, a serious event, an event that led to discontinuation of study drug, and an event that led to withdrawal from the study, repeated also by age at symptom onset
- incidence by primary system organ class and preferred term, repeated also by age at symptom onset
- Frequency of adverse events by system organ class and preferred term, repeated also by age at symptom onset
- incidence of mild, moderate and severe events by primary system organ class and preferred term
- incidence of severe events by primary system organ class and preferred term
- incidence of not related, unlikely to be related, possibly related, and related events by primary system organ class and preferred term
- incidence of drug-related events by primary system organ class and preferred term
- incidence of SAEs by primary system organ class and preferred term and a listing of SAEs
- incidence of death and a listing of each death
- incidence of events that led to death
- incidence of events leading to discontinuation of study drug by primary system organ class and preferred term and a listing of such events
- incidence of events leading to withdrawal from the study by primary system organ class and preferred term and a listing of such events
- incidence of events of special interest – AEs following dosing procedure/LP, AEs by antibody status etc., by primary system organ class and preferred term and a listing of such events.

To avoid the potential for misleading interpretation of analysis of AEs, no statistical testing will be performed.

Only the following presentations will be shown for Part 2 analysis:

- an overall summary showing, the number and percentage of subjects with an AE, a moderate or severe event, a severe event, a possibly or related event, a related event, a serious event, an event that led to discontinuation of study drug, and an event that led to withdrawal from the study
- incidence by primary system organ class and preferred term
- Incidence of serious adverse events by primary system organ class and preferred term and a listing of SAEs.
- Frequency of adverse events by system organ class and preferred term

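### The integrated AE and SAE tables set crude sham percentages from Part 1 alone beside nusinersen percentages from Part 1 plus Part 2, so longer follow-up alone can produce an apparent nusinersen excess

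*SAP*

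**What the plan says.** SAP Section 2 (Statistical Methods: General Considerations) lists four columns for the integrated safety displays. Two concern us here: "Previous control, Part 1, from their first sham procedure in Part 1" and "Previous ISIS 396443, Part 1 and 2, from their first ISIS 396443 dose in Part 1". The others are previous control in Part 2 and a total that combines previous control in Part 2 with previous nusinersen in both parts. None shows nusinersen over Part 1 alone.

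The same section records that "subjects randomized to sham terminated Part 1 first irrespective of Part 1 planned dosing days", while nusinersen subjects moved into Part 2 on their own dosing schedule.

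Section 5.1 counts a child once per AE however often it recurs, and adds: "Due to the long half-life of Nusinersen, analyses of treatment-emergent AEs will include all events reported during the study". Section 5.1.6 asks for "an overall summary showing, the number and percentage of subjects with an AE", followed by incidence by system organ class and preferred term, event frequencies, and a statement that AEs will not be tested.

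Three provisions bear on follow-up:
- Section 5.1.3: "The incidence of treatment-emergent SAEs will be summarized by time of onset by 3-month time intervals".
- Section 3.3: "The dosing and time on study will be summarized only for Part 2 and integrated data".
- Section 1: "the planned analysis of Part 1 is described in a separate Statistical Analysis Plan and corresponding CSR".

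Protocol Section 16 defines a pooled safety analysis that takes sham-randomised children from Part 2 only, so it has no sham Part 1 column.

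**The concern.** The percentage of children with at least one event cannot fall as follow-up lengthens. Here one column stops at the end of Part 1, which sham children left first, and the other continues through Part 2. Anyone opening the integrated report will read across from sham to nusinersen, because sham Part 1 is the only untreated experience in the table. With no drug effect at all, the nusinersen column would still tend to be higher for events of intermediate frequency.

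Incidence of AEs and SAEs heads the list of primary endpoints for both parts (protocol Section 6.1). The bias makes nusinersen look less safe. Because its size is unknown, it also makes a real difference hard to judge.

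The SAP deals with unequal time elsewhere. It builds opportunity-to-be-assessed denominators for by-visit efficacy (Section 4.1), prorates ventilator hours by days on study (4.2.1), and uses Kaplan-Meier with censoring for death or permanent ventilation (4.2.2). AE incidence gets nothing equivalent.

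**Working it through.** The documents state no AE rate, no power calculation and no actual follow-up, so there is no planned figure to reproduce. The event rates below are assumptions.

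**Inputs from the documents**
- Planned end of Part 1: Day 422 (protocol Section 7.2.3).
- Planned Part 2 final visit, nusinersen arm: Part 2 Day 835 (protocol Table 3). Planned nusinersen follow-up is 422 + 835 = 1257 days.
- Planned numbers: 14 nusinersen, 7 sham. One sham child is 1/7 = 14.3 points.
- Both parts ended early, with no days given (SAP Sections 1, 1.3 and 2). Two shorter pairs are therefore assumed: 302 against 778 days, and 422 against 540 days.

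**Model.** The same constant rate r of first events per patient-year applies in both columns. The chance of an event by day d is 1 − exp(−r·d/365.25). With d1 days for sham and d2 for nusinersen:

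gap = exp(−r·d1/365.25) − exp(−r·d2/365.25)

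The gap is largest at r = 365.25 · ln(d2/d1)/(d2 − d1).

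| Follow-up, sham vs nusinersen (days) | Ratio | r at largest gap (per year) | Sham | Nusinersen | Gap (points) |
|---|---|---|---|---|---|
| 422 vs 1257 (planned maximum) | 2.98 | 0.48 | 42.4% | 80.7% | 38.3 |
| 302 vs 778 (assumed) | 2.58 | 0.73 | 45.1% | 78.7% | 33.6 |
| 422 vs 540 (assumed) | 1.28 | 0.76 | 58.6% | 67.6% | 9.0 |

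**Rare and near-universal events, planned follow-up.** Nusinersen % = 1 − (1 − sham %)^2.98. A sham risk of 2% gives 5.8%, a gap of about 4 points. At 3 first events per year the columns read 96.9% and 100.0%, a gap of about 3 points. The problem lies in the middle of the range.

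**Chance of being misled with 7 and 14 children.** Exact binomial enumeration, equal event rates, sham risk 20%:

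| Follow-up (days) | P(nusinersen % higher) | P(excess of 20 points or more) |
|---|---|---|
| 422 vs 1257 | 89% | 71% |
| 302 vs 778 | 84% | 63% |
| 422 vs 540 | 54% | 25% |
| 422 vs 422 | 44% | 17% |

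**Whole-period rates are not a complete repair.** By schedule the sham column has 6 procedures in 422 days: 6/422 × 365.25 = 5.2 per year. The nusinersen column has 6 + 7 = 13 in 1257 days: 13/1257 × 365.25 = 3.8 per year, about 27% lower. A rate over the whole period would dilute procedure-related AEs in the nusinersen column. Matching the period should therefore come first, with rates as a supplement.

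**The case against.** The best counter-argument is that the randomised comparison belongs elsewhere. Protocol Section 16 has the two parts analysed separately and AEs summarised by treatment group, and the SAP refers Part 1 to its own plan and report. On that reading, the integrated display describes long-term safety. Its total column is exactly the protocol's pooled population, and sham Part 1 is a labelled reference outside it. Time on study will be summarised, SAEs are split by onset interval, AE frequencies are tabulated as well as incidence, nothing is tested, the study is exploratory, and the bias would not conceal a harm.

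Much of this is fair. The pooled population is preserved, and a matched comparison may well exist in the Part 1 report, which is not among the documents available here. The column labels do show that the periods differ. The planned durations are an upper scenario, and at 422 against 540 days the artefact is small. Constant hazard overstates the gap for events clustered after the early procedures.

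None of it corrects the adjacent percentages. Time on study appears in a separate table and is not a denominator. The onset split covers SAEs only and names no number at risk. Event frequencies also lack person-time. Leaving out tests does not stop a reader from comparing columns. The procedure-density figures are a caution about rates and do not equate the two procedures: the sham is a skin prick, not a lumbar puncture.

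**Conclusion.** The concern holds. Followed as written, the integrated AE and SAE incidence tables contain a follow-up artefact in the sham-to-nusinersen comparison, always in the direction of a nusinersen excess. It is material for events of intermediate frequency and minor for rare or near-universal ones.

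The size cannot be fixed from the documents. Under equal constant hazards the largest gap is 38 points at full planned follow-up, 34 points under one assumed early stop and 9 points under a mild one. Actual follow-up decides where the study falls. Events that become more likely with age or disease progression would inflate more than this model suggests, and events clustered early would inflate less.

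This should be changed because it touches a primary endpoint display and the repair is cheap. It does not threaten the conduct of the study or its randomised Part 1 analysis.

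**What to change.** In the integrated AE and SAE tables:

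1. Add a previous-nusinersen, Part 1 column as the comparator for the sham Part 1 column. Preferably cut both at one follow-up day fixed before the tables are run, because sham children left earlier.
2. Show median follow-up and patient-years for every column, using the time on study already derived under SAP Section 3.3.
3. Add children with the event per patient-years to first event, as a supplement to the percentages. This also covers sham children who left before the common day.
4. Give the number at risk in each interval of the 3-month SAE table.
5. State that the matched-period columns carry the sham comparison, that the combined-parts column only describes long-term safety, and that whole-period rates are affected by procedures being concentrated early.

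The cost is wider tables and some programming on data already collected. A common cut-off leaves later sham events out of the matched column, and the rate summary assumes a roughly constant hazard, which the early loading procedures strain.
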